4. OBJECTIVE(S)/SPECIFIC AIMS AND HYPOTHESES

- *A concise statement of the goal(s) of the current study.*
- *The rationale for and specific objectives of the study.*
- *The goals and the hypothesis to be tested should be stated.*

The objective of this study is to compare readmission rates and compliance with follow-up appointments among patients who are shown the 3D rendering of their ultrasound compared with a historical cohort of patients who viewed 2D based sketches of their vasculature. We hypothesize that patients receiving the 3D ultrasound would have higher compliance with follow-up appointments and lower

readmission rates compared with patients who did not have a 3D rendering of their study created because patients in the 3D subset would be better able to visualize their affected blood vessels and understand disease severity.

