6. RECRUITMENT METHODS

- *Describe the source of potential subjects*
- *Describe the methods that will be used to identify potential subjects*
- *Describe any materials that will be used to recruit subjects. A copy of any advertisements (flyers, radio scripts, etc.) should be submitted along with the protocol.*
- *If monetary compensation is to be offered, this should be indicated in the protocol*

Participants will be recruited from the wound center's patient population. The wound center's vascular suite performs 10-15 ultrasound studies on a daily basis. These patients are experiencing symptoms of vascular insufficiency. There are various anatomical locations that are studied with ultrasound and therefore subjects will be grouped for analysis. These patients will be approached to enroll in the study. No materials will be used to recruit subjects. Subjects will not be offered compensation to participate.

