7. ELIGIBILITY CRITERIA

- *Describe the characteristics of the subject population, including their anticipated number, age, ranges, sex, ethnic background, and health status. Identify the criteria for inclusion or exclusion of any subpopulation.*
- *Explain the rationale for the involvement of special classes of subjects, such as fetuses, pregnant women, children, prisoners or other institutionalized individuals, or*

others who are likely to be vulnerable. You cannot include these populations in your research, unless you indicate such in the protocol

- *Similarly, detail exclusionary criteria: age limits, special populations (minors, pregnant women, decisionally impaired), use of concomitant medications, subjects with other diseases, severity of illness, etc.*

INTERVENTIONAL COHORT:

Inclusion:

- Age 18 years of age or older
- Suspected vascular insufficiency that requires ultrasound evaluation
- Subject is able to sign a consent form
- Scheduled ultrasound testing at the wound center to evaluate vasculature

Exclusion:

- Younger than 18 years old
- Subject is not scheduled to have ultrasound testing at the wound center
- Subject is unable to or refuses to consent to participate

RETROPECTIVE COHORT:

Inclusion:

- Age 18 years of age or older
- Subjects who have undergone vascular ultrasound testing at the wound center
- Ultrasound tests performed from 1/1/2019-12/31/2019
- Subjects who were followed by the wound center team after undergoing ultrasound testing for vascular insufficiency

Exclusion:

- Younger than 18 years old
- Subjects who underwent testing outside the above mentioned timeframe
- Subjects who were not followed by the wound center team after undergoing ultrasound testing for vascular insufficiency

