9. STUDY TIMELINES

- *Describe the duration of an individual's participation in the study*
- *Describe the duration anticipated to enroll all study subjects*
- *The estimated date of study completion*

The duration of an individual's participation will last as long as it takes to perform their scheduled ultrasound testing. Ultrasound testing usually takes no more than 30 minutes. Enrolled subject's EMR will be reviewed for 6 months after they undergo the ultrasound testing. We anticipate it will take 6-8 months to enroll all study subjects.

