10. ENDPOINTS

- *Describe the primary and secondary study endpoints*
- *Describe any primary or secondary safety endpoints*

The primary endpoint of the study will be the treatment outcomes for the patients. We will review readmission rates (30 days from the day of the ultrasound) as well as compliance to first follow-up appointment after the ultrasound of interventional cohort. These endpoints will be compared to those of a historical cohort of persons who were treated for similar pathologies in the past.

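### The historical 2D cohort is selected on follow-up after the ultrasound, which overlaps the compliance endpoint, and the 3D cohort is not

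*Protocol*

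**What the plan says.** The retrospective list in Protocol section 7 requires "Subjects who were followed by the wound center team after undergoing ultrasound testing for vascular insufficiency". The matching exclusion removes "Subjects who were not followed by the wound center team after undergoing ultrasound testing for vascular insufficiency". The term *followed* is not defined.

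The interventional list has no such condition. Apart from age, suspected insufficiency and ability to consent, it asks only for "Scheduled ultrasound testing at the wound center to evaluate vasculature". Section 23 places consent before the scan, and section 6 gives the source: "Participants will be recruited from the wound center's patient population".

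Section 4 describes the comparator as "a historical cohort of patients who viewed 2D based sketches of their vasculature" and hypothesizes that "patients receiving the 3D ultrasound would have higher compliance with follow-up appointments". Section 10 lists, under the primary endpoint and beside 30-day readmission, "compliance to first follow-up appointment after the ultrasound of interventional cohort". Section 12 tests the proportion attending, 3D against 2D, by chi-square, and allows multivariable regression for baseline differences if warranted.

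**The concern.** Whether a patient was followed after the scan is known only after the scan, and it is close to what the compliance endpoint measures. Applied to the historical cohort alone, the rule can remove 2019 patients because they did not come back, while 3D patients who do not come back are kept and counted as failures. The two proportions in the chi-square test would then have different denominators, one of them selected partly on the outcome.

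The comparison of follow-up attendance is at stake. It is part of the objective and the hypothesis, and section 10 places it under the primary endpoint. A real 3D benefit could be hidden or appear reversed, and with no true effect the 2D sketch could appear better. The comparator in section 4, patients who viewed 2D sketches, does not call for this restriction.

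**Working it through.** **The plan's own figure.** Section 8 gives 135 per group for readmission of 10% against 2%, 80% power and 95% confidence. The two-sided formula with unpooled variance gives (1.960 + 0.842)² × (0.10×0.90 + 0.02×0.98) / 0.08² = 134.4, that is 135. The pooled version gives 138. The figure reproduces. It rests on readmission only, and the protocol gives no attendance rate.

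**Inputs for the compliance comparison.** From the protocol: 135 per group and the chi-square test. Assumed: a two-sided 0.05 level; true 2D attendance *a*; true 3D attendance *b*; and *r*, the chance that a patient who missed the first visit counts as followed, divided by the same chance for an attender. With all attenders counted, *r* is simply the share of missers retained.

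**Observed 2D attendance** = a / (a + (1 − a)r). For a = 0.70 and r = 0.50: 0.70 / (0.70 + 0.30×0.50) = 0.70/0.85 = 82.4%. A true 3D rate of 80% then shows as 80.0 − 82.4 = −2.4 points instead of +10.

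**Rejection probabilities** come from exact enumeration of two binomials (135 and 135) with the uncorrected chi-square test. For a = 70%:

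| r | Observed 2D attendance | Significant for 3D (true 3D 80%) | Significant for 2D (true 3D 80%) | Significant for 2D (no true effect, both 70%) |
|---|---|---|---|---|
| 0% | 100% | 0% | 100% | 100% |
| 25% | 90% | 0% | 67% | 99% |
| 50% | 82% | 0.7% | 7.2% | 67% |
| 75% | 76% | 14% | 0.3% | 18% |
| 90% | 72% | 33% | 0% | 6% |
| 100% | 70% | 48% | 0% | 2.5% |

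Other assumed rates, r = 0, 25, 50, 75, 90, 100%:
- 60% vs 70%, significant for 3D: 0, 0, 0.2, 8.5, 25, 41%. No effect at 60%, significant for 2D: 100, 99.8, 75, 21, 6.4, 2.6%.
- 80% vs 90%, significant for 3D: 0, 0.1, 4.8, 29, 51, 64%. No effect at 80%, significant for 2D: 100, 95, 53, 15, 5.3, 2.6%.

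**Break-even.** The observed difference changes sign when observed 2D attendance equals *b*, that is r = a(1 − b) / (b(1 − a)):
- 60 vs 70: 0.60×0.30 / (0.70×0.40) = 0.643
- 70 vs 80: 0.70×0.20 / (0.80×0.30) = 0.583
- 80 vs 90: 0.80×0.10 / (0.90×0.20) = 0.444

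Below these values a true 10-point benefit is expected to show as a deficit. Above them, and up to r = 100%, the effect is lost power.

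**Can the planned adjustment repair it?** No. Regression on baseline covariates works on patients in the dataset, and the excluded non-attenders are not in it.

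**The case against.** The strongest reply is that *followed* may only mean under the team's care. Section 10 describes the comparator as people treated for similar pathologies, and section 24 says many of them are no longer under the researchers' care, which implies that they once were. The line may be the retrospective counterpart of section 6, which draws 3D participants from the center's own patients. On that reading most non-attenders stay and the bias is small, or zero at r = 100%. This stands as a possibility. But the protocol leaves the choice to whoever abstracts the charts, and the wording looks forward from the scan. Even the mild reading is applied after the scan and to one cohort.

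Second, sections 8 and 12 name readmission alone as primary, and no effect on readmission is claimed here. That is correct, and the sized analysis is not challenged. Compliance nonetheless remains in the hypothesis, the objective and the primary endpoint of section 10.

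Third, the bias works against the hypothesis, so it should not create a false 3D benefit. That holds while r is at most 1. If patients seen once and discharged did not count as followed, r could exceed 1 and the direction would turn. A hidden benefit or a spurious 2D advantage is still a wrong answer.

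Fourth, the sizes rest on assumed rates, and the extreme rows need a low r. This stands. At r = 90%, with 70% vs 80%, power falls only from 48% to 33%.

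**Conclusion.** The concern holds and should be corrected before the historical charts are abstracted. It is certain from the text that one cohort is selected on an event after the ultrasound that overlaps the attendance endpoint, and that the other is not. The size is not known. Over the assumed rates (60 to 80% in 2D, a true 10-point gain, 135 per group), the consequence runs from none at r = 100%, through lost power, to a reversed result once r falls below about 44 to 64%. The direction, against 3D, assumes that missers are no more likely than attenders to count as followed. Consent selection in the 3D cohort may push the other way, so the net direction of all biases is undetermined. Any effect on readmission is left open.

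**What to change.** Delete the inclusion and exclusion lines on being followed. Define both cohorts by the same criteria known at or before the scan, for example wound-center patients with a scheduled vascular ultrasound.

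For compliance, use as denominator in both cohorts every patient for whom a first follow-up appointment after the ultrasound was ordered or scheduled, kept or not, and count non-attenders as non-compliant. Ordering an appointment is itself a step after the scan and may differ between periods, so report the share with an appointment ordered in each cohort. Apply the same record-review window to both: section 9 says "EMR will be reviewed for 6 months after they undergo the ultrasound testing", but only of enrolled subjects.

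The cost is a short amendment to eligibility and endpoints, and a chart-review field for appointments made but not kept. The 135 per group is unchanged, since it rests on readmission. The historical attendance rate will probably be lower than under the present rule. The change does not remove consent selection or calendar-time differences between the cohorts.

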8. NUMBER OF SUBJECTS

- *Indicate the total number of subjects to be accrued locally. If applicable, distinguish between the number of subjects who are expected to be pre-screened, enrolled (consent obtained), randomized and complete the research procedures.*
- *If your study includes different cohorts, include the total number of subjects in each cohort.*
- *If this is multisite study, include total number of subjects across all sites.*

The total number of subjects we plan to enroll is 270. We plan to enroll 135 subjects into the 3D imaging cohort of this study. Another 135 patients will be identified retrospectively for the historical cohort.

The sample size calculation was based on the primary outcome of 30-day readmission. We assumed a readmission rate of 10% in the 2D group and a readmission rate of 2% in the 3D group. We would need 135 patients in each group to have 80% and a confidence level of 95% to detect this difference.

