5. RESOURCES AVAILABLE TO CONDUCT THE HUMAN RESEARCH

- *Explain the feasibility of meeting recruitment goals of this project and demonstrate a potential for recruiting the required number of suitable subjects within the agreed recruitment period*
 - *How many potential subjects do you have access to?*
- *Describe your process to ensure that all persons assisting with the trial are adequately informed about the protocol and their trial related duties and functions*

The wound center has a vascular suite in which 10-15 vascular ultrasound tests are performed on a daily basis. The vascular suite has its own ultrasound machine. Potential subjects will be recruited from the pool of patients who have been scheduled to undergo ultrasound testing of their vasculature. The ultrasound technologists will be instructed in how to use the device. The method and technique of performing the test will not be altered in any way. The tech will perform the standard vascular testing as designated by the clinician who ordered the test.

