24. WAIVER OR ALTERATION OF THE CONSENT PROCESS

N/A

Complete this section if you are seeking an alteration or complete waiver of the consent process.

- *Describe the possible risks of harm to the subjects involved in this study and explain why the study involves no more than minimal risk to the subject:*
- *Explain why the waiver/ alteration will not adversely affect the rights and welfare of subjects*
- *Explain why it is impracticable to conduct this research if informed consent is required*
- *Explain why it is not possible to conduct this research without using the information or biospecimens in an identifiable form*
- *If appropriate, explain how the subjects will be provided with additional pertinent information after participation. If not appropriate to do so, explain why.*

In regards to the RETROSPECTIVE COHORT:

This study poses minimal risk of harm to subjects within this cohort as the intervention to be studied has already occurred. The subject consented to undergoing the vascular study at that time. Our research team will access these subject charts to collect information regarding the results and outcomes of these subjects after their vascular studies were performed.

The waiver of consent will not adversely affect subject's rights and welfare because there is no clinical intervention and/or assessment being made on these subjects. The intervention in question has already been performed on the

subject to which they consented to at the time of the procedure. Inclusion in the study will not affect their care in any form.

Requiring informed consent for this cohort would be impracticable because many subjects who qualify for this cohort are no longer under the care of the researchers. In addition, tracking down and locating these subjects in order to have a consent form delivered and signed would create a significant logistical challenge. Finally, the creation of a consent form would then create the only traceable paper trail linking the subjects to the study. All other records of these subjects are digitized and will be accessed via EMR.

Identifiable information is required to perform the data collection. To ensure accuracy and quality of the data, subject records may be accessed more than once. Once the data collection phase is complete, all identifiers will be permanently erased from the database. The final dataset to be analyzed will not contain any PHI.

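### The plan gives no rule for drawing the 135 historical controls from the 2019 patients and does not blind the selector to outcomes already in the chart

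*Protocol*

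**What the plan says.** Protocol Section 8 sets two groups of equal size. For the prospective arm: "We plan to enroll 135 subjects into the 3D imaging cohort of this study". For the comparator: "Another 135 patients will be identified retrospectively for the historical cohort".

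The retrospective criteria in Section 7 define who may enter: adults, scanned at the wound center, within a fixed window ("Ultrasound tests performed from 1/1/2019-12/31/2019"), and subsequently under follow-up by the center's team. Section 10 describes the comparator as a "historical cohort of persons who were treated for similar pathologies in the past", without defining similarity.

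Section 5 gives the workload of the vascular suite: "10-15 vascular ultrasound tests are performed on a daily basis". Section 24 describes how the control data are obtained: "Our research team will access these subject charts to collect information regarding the results and outcomes".

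Section 12 compares 30-day readmission and follow-up attendance by chi-square tests, groups the analysis by ultrasound type, and allows regression adjustment for baseline differences if this is judged necessary.

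The protocol states no consecutive, random or matched draw, no index scan for a patient scanned more than once in 2019, and no blinding of whoever chooses the controls.

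**The concern.** The frame is defined, but the step from the frame to 135 patients is not. If many more than 135 patients qualify, someone has to choose, and both endpoints are already recorded in the charts that will be opened. A convenience sample, or one chosen with outcomes in view, would comply fully with the protocol.

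The control rate is one of only two numbers in the primary comparison. An upward shift in it produces an apparent 3D benefit; a downward shift hides a real one. The adjustment in Section 12 works on baseline characteristics. It can address differences in a measured factor such as ultrasound type, but it cannot repair a sample whose membership depends on the outcome itself.

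This is a design matter. It decides who is in the study, it belongs with the eligibility and sample-size sections that already define this cohort, and charts could be chosen before any analysis plan applies.

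**Working it through.** **1. The plan's own figure.** Section 8 states: "We assumed a readmission rate of 10% in the 2D group and a readmission rate of 2% in the 3D group", and "We would need 135 patients in each group to have 80% and a confidence level of 95% to detect this difference". I read this as 80% power and two-sided alpha 0.05. With unpooled variance,

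n = (1.960 + 0.842)² × (0.10×0.90 + 0.02×0.98) / (0.10 − 0.02)² = 7.849 × 0.1096 / 0.0064 = 134.4, so 135 per group.

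The sample size reproduces and is not at issue.

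**2. Size of the pool.** The documents give no 2019 count. Assume the daily volume in Section 5 applied in 2019, over about 250 working days:

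- 10 × 250 = 2,500 scans; 135 / 2,500 = 5.4%
- 15 × 250 = 3,750 scans; 135 / 3,750 = 3.6%

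These are scans. Repeat scans and the post-scan follow-up criterion reduce the number of eligible patients by an unknown amount. If only one fifth qualified (assumed), the pool would be 500-750 patients, and 500/135 = 3.7 to 750/135 = 5.6 times the number needed. A choice is still required.

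**3. Effect of a selected control rate when 3D does nothing.** Inputs: 135 per group, chosen controls at the plan's 10%, and a true rate in both periods (and so in the 3D group) of 10%, 8%, 7% or 6%. The gaps of 2-4 points are hypothetical. The probability is the sum, over all pairs of counts (a controls, b 3D) with a > b and chi-square above 3.84, of Bin(a; 135, 0.10) × Bin(b; 135, true rate).

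| True rate | False 3D benefit, uncorrected chi-square | With continuity correction |
|---|---|---|
| 10% (no selection) | 2.5% | 1.5% |
| 8% | 8.3% | 5.4% |
| 7% | 14.1% | 9.6% |
| 6% | 22.7% | 16.2% |

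Section 12 does not say whether a correction is applied, so both are shown.

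**4. Selection in the other direction.** If 3D truly gives 2%, the same exact calculation (uncorrected) gives power of 83% with controls at 10%, 64% if the chosen controls run at 8%, and 38% at 6%.

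**5. Does anything else in the protocol close the gap?** Section 7 narrows the frame but does not draw from it. The similarity wording in Section 10 is undefined. The adjustment in Section 12 is conditional and limited to baseline differences. Section 24 confirms that outcomes come from existing charts and says nothing on the order of selection and abstraction.

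**The case against.** The strongest reply is that the protocol does restrict the control group, by age, site, calendar year and follow-up by the team; that it plans analysis by ultrasound type; and that it provides for adjustment. A reader might infer that the similarity wording in Section 10 is the only selection criterion. Section 7 shows otherwise. What is missing is the draw within the frame.

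Several other stronger readings also fail:

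- **That the team plans to choose controls with outcomes in view.** The documents do not say who selects, or in what order. The text permits outcome-aware selection but does not plan it.
- **That 2,500-3,750 eligible patients exist.** That figure counts scans, under an assumed number of days and a present-tense volume.
- **That one control chart decides the trial.** With 3 readmissions in the 3D group, 10 control readmissions are significant (p=0.047) and 9 are not. Any threshold with small counts behaves this way, even under perfect random sampling, and with continuity correction 12 are needed. This is not evidence of selection bias.
- **That season or scan-type mix will distort the result beyond repair.** Both are measurable. Nothing in the documents links season to readmission, and no type mix is given from which to predict sparse groups.

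It can also be said that the sampling mechanics may sit in an analysis plan or abstraction manual. That is a weak defence for a cohort that Sections 7 and 8 already set out to define.

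What survives all of this is the absence of a draw rule and of blinding to outcome. Conditional baseline adjustment does not answer either.

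**Conclusion.** The point stands in this limited form and should be corrected before any control chart is opened. The protocol fixes a 2019 frame but neither a method for drawing 135 patients from it nor any protection against seeing outcomes while choosing.

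The conclusion that a choice must be made assumes that the eligible pool exceeds 135. This is very likely from the stated workload, but is not documented. The sizes in the working show what a shift of 2-4 points would do; they do not estimate a bias that will occur, and the shift could go either way. The 135 per group is correctly derived and unaffected.

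**What to change.** Amend Sections 7 and 8 as follows.

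1. List every patient scanned in the vascular suite in 2019 from the scan log, with one index scan per patient chosen by a stated rule.
2. Draw 135 by a seeded random sample, or consecutively from a fixed start, stratified to the ultrasound-type mix of the 3D cohort. Matching on calendar month is not advised: it would spread 135 patients over too many small cells.
3. Define follow-up by the center's team so that it does not depend on attending the first appointment after the scan. Otherwise, eligibility overlaps the attendance endpoint, and checking it reveals that endpoint.
4. Check eligibility in draw order, by someone without sight of readmission or attendance. Replace an ineligible patient only by the next in the draw.
5. Lock the list before outcomes are abstracted.

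The cost is protocol wording, a scan-log export, and screening of somewhat more than 135 charts, because some drawn patients will prove ineligible. The draw has to wait until the 3D type mix is known, or be made in blocks as enrolment proceeds. The number analysed stays at 135 per group.
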